- 9. At 48 (-/+5) hours post-vaccination the team will call the fourth participant and go through their diaries. If the reactions are Grade 1-2, or transient Grade 3 that resolve within 24 hours, the fifth participant may receive 5 μ g of LNP-MARVsaRNA plus 4 μ g of LNP-EBOVsaRNA plus 4 μ g of LNP-LASSAsaRNA

- 10. At 1 day post immunisation, the fifth participant will attend the trial site to review AEs and donate blood to measure innate immune responses.
- 11. At 48 (–/+5) hours post-vaccination the team will call the fifth participant and go through their diaries. If the reactions are Grade 1-2, or transient Grade 3 that resolve within 24 hours, the dose evaluation cohort of remaining 35 participants may start to be enrolled and randomised into one of the 5 groups to receive their first immunisation.
- 12. Sentinel participants will be evaluated again as above after receiving their second dose. If the reactions are Grade 1-2, or transient Grade 3 that resolve within 24 hours, the cohort of remaining 35 participants may receive their second dose

The steps above describe the fastest plan to enrol into the 5 groups and is justified based on previous experience with this self-amplifying RNA platform. However, if there are persistent Grade 3 reactions observed in any of the sentinels, the team will invite the affected participant to attend the trial site in order to evaluate these and will proceed to vaccinate a second sentinel within the same group. The group will not be changed until at least 1 participant has provided acceptable safety data to at least 48 (–/+5) hours post-vaccination. If 2 or more of the participants at any dose level in this part of the trial have persistent Grade 3 (or worse) reactions, or if 1 or more has a serious adverse reaction, the dose will not be expanded, and the trial stopping rules described below (7.1.5) will be triggered.

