7.1.5 Dose Modifications For Toxicity & Schedule Interruptions

Target visit dates (based on the enrolment date) should be adhered to as far as possible, based on the allowable window (detailed in Table 2). The schedule may be interrupted if a participant has symptoms or signs on the day of scheduled injection, and the investigator considers it best to defer the injection. A temperature over 37.5°C would prevent injection on the day. Clinicians should consult the PI/Medical Delegate if there are any Grade 1 (mild) symptoms or signs listed in **Table 4**. The participant will be asked to return for review within the ideal window period of the scheduled injection. Provided the injection is administered during the window period outlined in the paragraph below for missed visits, this will not be a protocol deviation.

The PI or Medical Delegate should interrupt the vaccine schedule and inform the Chief Investigator within 24 hours using the safety email if there is a confirmed:

Grade 3 (severe) or worse solicited adverse event that has persisted for more than 72 hours regardless
of relationship

or

- other Grade 3 (severe) or worse adverse event that is possibly, probably or definitely related to vaccine or
- serious adverse reaction regardless of grade

The Chief Investigator/Delegate may recommend further investigations or referral to an independent expert to support the clinical management of the participant. Such events are highly likely to result in discontinuation, but a decision to resume will be taken by the PI with the participant, and only with the approval of the independent members of the TSC.

Injections for all participants will be paused pending a review of all safety data by the Trial Steering Committee if two participants out of 20, and the equivalent (10%) thereafter develop persisting Grade 3 (severe) adverse reactions within 7 days of immunisation, or any participant experiences a serious adverse reaction at any time. Approval of an amendment from the competent authorities is required before the trial can be resumed.

If two participants in any Group experience a Grade 3 reaction the trial will be paused and only resumed after approval of a substantial amendment.

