8.1.4 OTHER NOTABLE EVENTS

Notable adverse events which impact on the injection schedule and therefore require expedited (within 24 hours of the investigator becoming aware of the event) reporting whether or not they meet the serious criteria include:

- Grade 3 (severe) and above solicited adverse events which last more than 72 hours and Grade 3
 and above laboratory adverse events that are confirmed on repeat testing if possible
- Any adverse event leading to a clinical decision to interrupt or discontinue the injection schedule
- Pregnancy within 18 weeks of an injection

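### Both trial-level pause limits in Protocol 7.1.5 name Grade 3 only, while the linked hold, sentinel and reporting rules cover Grade 3 and above, so read literally a non-serious Grade 4 reaction is not counted

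*Protocol*

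**What the plan says.** Protocol 7.1.5 works at two levels.

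- **Individual hold.** The schedule is interrupted for a "Grade 3 (severe) or worse solicited adverse event that has persisted for more than 72 hours", whatever its relationship to vaccine. It is also interrupted for any other adverse event of Grade 3 or worse that is at least possibly related, and for a serious adverse reaction of any grade.
- **Trial-level pause.** Injections stop for everyone once a set number of participants "develop persisting Grade 3 (severe) adverse reactions within 7 days of immunisation". That number is two of 20, then 10%. A single serious adverse reaction has the same effect. A second limit works by group: "If two participants in any Group experience a Grade 3 reaction the trial will be paused".

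Two neighbouring rules also state a grade range. In 4.1.1, two or more participants at a dose level in the sentinel part who "have persistent Grade 3 (or worse) reactions" prevent expansion and trigger the 7.1.5 stopping rules. In 8.1.4, expedited reporting applies to "Grade 3 (severe) and above solicited adverse events which last more than 72 hours", whether or not the event is serious.

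Section 11 adds another all-participant pause, at 2 of 8 participants and 25% thereafter, for similarly severe adverse reactions. It names no grade.

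**The concern.** Elsewhere in these rules the protocol adds words such as *or worse* or *and above* when it means a range of grades. Both trial-level limits in 7.1.5 lack them. A literal reader would therefore count a Grade 3 reaction toward a pause of the whole trial and leave a Grade 4 reaction out, unless the Grade 4 reaction is also serious.

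This is a first-in-human trial without an independent data monitoring committee. Section 4 promises clear thresholds for pausing, and under 7.1.5 a pause is lifted only after an approved amendment. Whether a limit has been crossed should therefore be a matter of counting. As written, two people applying 7.1.5 to the same data could disagree on the count.

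**Working it through.** **1. Grade range in each rule**

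| Rule | Section | Grades named |
|---|---|---|
| Individual hold, solicited event beyond 72 hours | 7.1.5 | 3 or worse |
| Individual hold, other related event | 7.1.5 | 3 or worse |
| Sentinel stop (triggers 7.1.5) | 4.1.1 | 3 or worse |
| Notable event, expedited report | 8.1.4 | 3 and above |
| Trial pause, 2 of 20 then 10% | 7.1.5 | 3 only |
| Trial pause, 2 in any group | 7.1.5 | 3 only |
| Trial pause, 2 of 8 then 25% | 11 | none stated |

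The stated percentages reproduce: 2/20 = 10% and 2/8 = 25%.

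**2. Does the serious-reaction limb close the gap?** Not fully. Seriousness (8.2.1) and severity grade (8.2.2) are assessed separately. The hold in 7.1.5 lists serious adverse reactions regardless of grade, and 8.1.4 requires reporting of Grade 3 and above whether or not the event is serious. The protocol therefore allows for a non-serious event above Grade 3.

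**3. Effect on the count.** Assume each reaction is non-serious and otherwise meets the condition of the limit, which for the 2-of-20 limit means persisting and starting within 7 days.

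| Two participants have | Count as written | Count if Grade 3 is a floor | Limit |
|---|---|---|---|
| Grade 3 and Grade 3 | 2 | 2 | 2 |
| Grade 3 and Grade 4 | 1 | 2 | 2 |
| Grade 4 and Grade 4 | 0 | 2 | 2 |

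The table applies to both 7.1.5 limits.

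**4. Illustration only.** The protocol gives no Grade 4 rate. Let p be an *assumed* proportion of participants with a non-serious Grade 4 reaction.

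- P(at least 2 of 20) = 1 − (1−p)^20 − 20p(1−p)^19
- P(at least 2 in one or more of five groups of 8) = 1 − [(1−p)^8 + 8p(1−p)^7]^5

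| Assumed p | At least 2 of 20 | At least 2 in any of five groups of 8 |
|---|---|---|
| 1% | 1.7% | 1.3% |
| 2% | 6.0% | 5.1% |
| 5% | 26.4% | 25.5% |

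A second view adds p to a Grade 3 rate of 2/24 = 8.3%, the systemic Grade 3 figure at 5 µg in Table 5. The chance of reaching 2 of 8 in one given group rises from 13.9% (Grade 3 only) to 16.7%, 19.7% or 29.0% for p = 1%, 2% or 5%. The chance of 2 of 20 rises from 50.5% to 56.9%, 62.7% or 76.7%. The 2-of-20 figures in both views ignore the persistence condition and so overstate how often that limit would be met.

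**The case against.** The best reply is that Grade 3 is obviously meant as a floor. Section 4.1.1 says two persistent reactions of Grade 3 or worse trigger the 7.1.5 rules, which would make little sense if 7.1.5 ignored the worse grade. That probably is the intent. However, the link covers only the sentinel part; for the remaining 35 participants the text of 7.1.5 stands alone.

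A reader might infer that Grade 4 reactions would go unseen and dosing would simply continue. The documents do not support that:

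- Many Grade 4 reactions may be serious. Table 4 covers life-threatening events, and its notes extend seriousness to important reactions that may jeopardise the participant or need intervention. One serious adverse reaction pauses the trial.
- Reactions that interrupt a schedule go to the TSC immediately, its independent members must approve any resumption, and it may recommend stopping all injections.
- Section 11 may catch two such reactions among eight. It states no grade and uses 25% rather than 10%, so two among 20 (10%) in different groups could satisfy neither rule as written.

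What is missing is an unambiguous count, not oversight.

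A reader might also infer that every non-serious Grade 4 reaction stops that person's injections. It does not: a solicited event must last beyond 72 hours, any other event must be at least possibly related, and the action is an interruption, although discontinuation is described as highly likely.

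Finally, the solicited-event hold ignores relationship while the 10% limit counts adverse reactions. That may look like a second contradiction. It is not: a precautionary hold for one person and a pause of the whole trial can reasonably use different criteria.

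**Conclusion.** The inconsistency is real and lies in a stated rule. Both trial-level limits in 7.1.5 name Grade 3 alone, whereas the hold in the same section, the sentinel stop that feeds it and 8.1.4 name Grade 3 and above. Read literally, two Grade 4 reactions not classed as serious count as 0 and a Grade 3 plus a Grade 4 counts as 1, against a limit of 2. The gap is confined to non-serious Grade 4 reactions and is narrowed by the serious-reaction limb, TSC review and possibly Section 11.

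How often it would matter cannot be estimated. The protocol gives no Grade 4 rate, Table 5 shows no Grade 4 row among 24 recipients at 5 µg, and the grading scale is external and not reproduced. The probabilities above are illustrations under assumed rates and the conclusion does not depend on them. It rests on the wording, and a safety threshold whose count turns on interpretation is worth correcting.

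**What to change.** The sponsor should reconcile the grade range used in the pause and stop rules across 7.1.5 (individual hold and both trial-level limits), 4.1.1, 8.1.4 and Section 11, so that the same event is either counted or not counted whichever section is consulted. Where a difference is intended, the text should say so. In the same edit, Section 11 should state which grades its similarly severe reactions cover and how its 2 of 8 (25%) relates to the 10% in 7.1.5. The thresholds and grades themselves are for the sponsor and clinicians to set.

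The cost is a few words in the next amendment and a matching line in the TSC report template. If the reconciled range is wider than the present literal one, a pause could occur somewhat more often.

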7.1.6 DISCONTINUATION OF INJECTIONS IN ALL PARTICIPANTS

Protocol planned interruptions and discontinuations will be reported to the Chief Investigator/Medical Delegate who will make a recommendation regarding immediate reporting to the TSC. The Chief Investigator and ICL staff responsible for preparing reports for the TSC will forward the clinical report and the dose allocation. All serious adverse reactions will be unexpected and reported on to the authorities (see section

8.3) by the Chief Investigator. The TSC may recommend to the Sponsor that injections are discontinued in all participants.

7.2 Treatment Data Collection

Study staff will collect vaccination information on the worksheets and enter data in the Electronic Data Capture (EDC) system. Pharmacy staff, or other staff delegated by the PI, will maintain the IMP accountability logs which will be securely stored.

7.2.1 Interactions with other Drugs and Vaccines

Non-trial treatments will be reviewed before each injection to ensure that the participant remains eligible and able to receive the vaccine. There are no known interactions between the LNP-MARVsaRNA, LNP-EBOVsaRNA or LNP-LASSAsaRNA vaccine and other drugs. All medications taken by participants from screening to the final visit will be recorded in the EDC system.

Participants should avoid taking systemic immunosuppressants, which might reduce their immune response to the vaccine.

Vaccination with authorised vaccines should be avoided from 28 days before screening until 28 days after the second injection because they may impact on the assessment of immune response to trial vaccine, and it is plausible that the self-amplification process is ongoing for this period of time.

7.2.2 CONCOMITANT THERAPIES

Systemic immunosuppressive agents, such as corticosteroids, may not be administered during the trial. Dermal steroids are permitted, but not if applied to the IM injection site.

Vaccination with authorised vaccines should be avoided from 28 days before screening until 28 days after the second injection, as they may affect the assessment of the immune response to the trial vaccine. It is plausible that the self-amplification process continues during this period.

7.3 Dispensing and Accountability

7.3.1 DISPENSING

The pharmacist, or other person delegated by the PI, will ensure that the vaccines are dispensed in accordance with the protocol and Pharmacy Manual and local procedures as appropriate. Local working instructions will be reviewed at site initiation, if applicable.

A vaccine accountability log will be kept to record the identification of the participant to whom the vaccine was given and the date they received it. Any damaged or unused vials that are returned will also be documented. The log will be checked during the monitoring visits and at the end of the trial.

7.3.2 ACCOUNTABILITY

The Pharmacist, or other person delegated by the PI, will ensure that all injection products are dispensed in accordance with the protocol, Pharmacy Manual and local procedures, and that records are maintained of receipt, dispensing and destruction of all supplies.

At the end of the trial, IMP accountability will be checked by the designated member of staff responsible for the inventory and by the trial monitors. The Sponsor and the PI will retain copies of the complete IMP accountability records and copies will be provided to the supplier of the vaccines.

All used vials of injections will be destroyed immediately after use in compliance with the instruction manual.

The site will be instructed to either return unused vaccine to the supplier, or to destroy it at site. Following IMP destruction, the pharmacist, or other person delegated by the PI, at the site must complete a certificate of IMP destruction and send it to the PI with copies to the Sponsor.

All injections will be administered by site staff and recorded on worksheets and in the Electronic Data Capture (EDC) system. If an injection is not given within the ideal window (see **Table 2**), this will be recorded in the EDC system together with the reason. Compliance with the schedule will be reviewed each week and reported to the TMG monthly.

8. PHARMACOVIGILANCE

[figure not shown]
The principles of GCP require that both investigators and Sponsors follow specific procedures when notifying and reporting adverse events or reactions in clinical trials. These procedures are described in this section of the protocol. **Section 8.1** lists definitions, **Section 8.3** gives details of reporting procedures. Collection of adverse event data must begin from the time that informed consent if given by the participant.

8.1 Definitions

The definitions of the EU Directive 2001/20/EC Article 2 based on the principles of GCP apply to this trial protocol. These definitions are given in **Table 4**.

Table 4. Definitions

TERM	DEFINITION	
Adverse Event (AE)	Any untoward medical occurrence in a patient or clinical trial subject administered a medicinal product and which does not necessarily have a causal relationship with this treatment.	
Adverse Reaction (AR)	All untoward and unintended responses to an IMP related to any dose administered.	
Unexpected Adverse Reaction (UAR)	an AR, the nature or severity of which is not listed in the reference safety information (RSI) e.g. list of expected medical events within investigator's brochure for an unapproved investigational product or section 4.8 of the summary of product characteristics (SmPC) for an authorised product.	
Serious Adverse Event (SAE) or Serious Adverse Reaction (SAR)	 characteristics (SmPC) for an authorised product. Any untoward medical occurrence or effect that at any dose: Results in death. Is life-threatening – refers to an event in which the subject was at risk of death at the time of the event; it does not refer to an event which hypothetically might have caused death if it were more severe. Requires hospitalisation, or prolongation of existing inpatients' hospitalisation. Results in persistent or significant disability or incapacity. Is a congenital anomaly or birth defect. 	
Suspected Unexpected Serious Adverse Reaction (SUSAR):	any suspected adverse reaction related to an IMP that is both unexpected and serious.	

- *The term life-threatening in the definition of a serious event refers to an event in which the patient is at risk of death at the time of the event; it does not refer to an event that hypothetically might cause death if it were more severe, for example, a silent myocardial infarction.
- **Hospitalisation is defined as an inpatient admission, regardless of length of stay, even if the hospitalisation is a precautionary measure for continued observation.
- *** Medical judgement should be exercised in deciding whether an AE or AR is serious in other situations. The following should also be considered serious: important AEs or ARs that are not immediately life-threatening or do not result in death or hospitalisation but may jeopardise the subject or may require intervention to prevent one of the other outcomes listed in the definition above; for example, a secondary malignancy, an allergic bronchospasm requiring intensive emergency treatment, seizures or blood dyscrasias that do not result in hospitalisation or development of drug dependency.

8.1.1 ADVERSE EVENTS

Adverse Events include:

- An exacerbation of a pre-existing illness
- An increase in frequency or intensity of a pre-existing episodic event or condition
- A condition (even though it may have been present prior to the start of the trial) detected after trial drug administration
- Continuous persistent disease or a symptom present at baseline that worsens following administration of the trial treatment

8.1.2 EXPECTED ADVERSE EVENTS

The safety and reactogenicity of the IMP is expected to be comparable to the safety observed in previous clinical trials conducted where saRNA have been tested with other vaccine antigens in Phase I clinical trials (COVAC1, COVAC Uganda). See summary table 5 below for systemic and local reactions reported in individuals who received a 5 µg dose of LNP-nCoVsaRNA vaccine.

Up to 100% of participants are expected to experience grade 1-2 systemic reactions including fatigue, myalgia, headaches, chills/shivering and arthralgia. Similarly, close to 100% of participants are expected to experience grade 1-2 local reactions, with pain and tenderness/discomfort likely to be the most common local reactions.

Uncommon reactions include high temperature (≥ 38°C), nausea and vomiting, and erythema and induration at site of injection.

Vasovagal syncope (i.e. fainting), may occur in this population of subjects. It will be attempted to minimise the occurrence of this reaction, by allowing the subjects to lie down during administration of vaccine and blood drawings.

Table 5. Adverse Events in participants the COVAC1 clinical trial who received a 5 μg dose of LNP-nCoV-saRNA

		LNP-nCoVsaRNA dose
		5.0 μg N=24
	Any	
	Normal	0 (0.0%)
	Grade 1	8 (33.3%)
	Grade 2	14 (58.3%)
	Grade 3	2 (8.3%)
	Temperature	
	Normal	21 (87.5%)
	Grade 1	2 (8.3%)
	Grade 2	0 (0.0%)
	Grade 3	1 (4.2%)
	Chills/shivering	
	Normal	10 (41.7%)
	Grade 1	11 (45.8%)
	Grade 2	3 (12.5%)
	Myalgia (flu-like general ı	
	Normal	5 (20.8%)
	Grade 1	13 (54.2%)
	Grade 2	6 (25.0%)
	Grade 3	0 (0.0%)
	Arthralgia	
0	Normal	11 (45.8%)
Systemic	Grade 1	9 (37.5%)
	Grade 2	4 (16.7%)
	Grade 3	0 (0.0%)
	Fatigue	
	Normal	3 (12.5%)
	Grade 1	11 (45.8%)
	Grade 2	10 (41.7%)
	Grade 3	0 (0.0%)
	Sidd 0	0 (0.070)
	Headache Normal	2 (9 20/)
	Grade 1	2 (8.3%) 14 (58.3%)
	Grade 2	8 (33.3%)
	Nausea Normal	19 (79.2%)
	Grade 1	5 (20.8%)
	Grade 2	0 (0.0%)
	Grade 3	0 (0.0%)
		(())
	Vomiting	
	Normal	24 (100.0%)
		24 (100.0%) 0 (0.0%)
	Normal Grade 3	0 (0.0%)
	Normal Grade 3 Any Normal	0 (0.0%)
	Normal Grade 3 Any Normal Grade 1	0 (0.0%) 1 (4.2%) 15 (62.5%)
	Normal Grade 3 Any Normal	0 (0.0%)
	Normal Grade 3 Any Normal Grade 1	0 (0.0%) 1 (4.2%) 15 (62.5%)
	Normal Grade 3 Any Normal Grade 1 Grade 2	0 (0.0%) 1 (4.2%) 15 (62.5%) 8 (33.3%)
	Normal Grade 3 Any Normal Grade 1 Grade 2	0 (0.0%) 1 (4.2%) 15 (62.5%)
	Normal Grade 3 Any Normal Grade 1 Grade 2 Pain Normal	0 (0.0%) 1 (4.2%) 15 (62.5%) 8 (33.3%)
	Normal Grade 3 Any Normal Grade 1 Grade 2 Pain Normal Grade 1 Grade 2	0 (0.0%) 1 (4.2%) 15 (62.5%) 8 (33.3%) 6 (25.0%) 16 (66.7%)
Local	Normal Grade 3 Any Normal Grade 1 Grade 2 Pain Normal Grade 1 Grade 2 Tenderness/discomfort	0 (0.0%) 1 (4.2%) 15 (62.5%) 8 (33.3%) 6 (25.0%) 16 (66.7%) 2 (8.3%)
Local	Normal Grade 3 Any Normal Grade 1 Grade 2 Pain Normal Grade 1 Grade 2	0 (0.0%) 1 (4.2%) 15 (62.5%) 8 (33.3%) 6 (25.0%) 16 (66.7%) 2 (8.3%)
Local	Normal Grade 3 Any Normal Grade 1 Grade 2 Pain Normal Grade 1 Grade 2 Tenderness/discomfort Normal	0 (0.0%) 1 (4.2%) 15 (62.5%) 8 (33.3%) 6 (25.0%) 16 (66.7%) 2 (8.3%)
Local	Normal Grade 3 Any Normal Grade 1 Grade 2 Pain Normal Grade 1 Grade 2 Tenderness/discomfort Normal Grade 1 Grade 2	0 (0.0%) 1 (4.2%) 15 (62.5%) 8 (33.3%) 6 (25.0%) 16 (66.7%) 2 (8.3%) 2 (8.3%) 14 (58.3%)
Local	Normal Grade 3 Any Normal Grade 1 Grade 2 Pain Normal Grade 1 Grade 2 Tenderness/discomfort Normal Grade 1	0 (0.0%) 1 (4.2%) 15 (62.5%) 8 (33.3%) 6 (25.0%) 16 (66.7%) 2 (8.3%) 2 (8.3%) 14 (58.3%)
Local	Normal Grade 3 Any Normal Grade 1 Grade 2 Pain Normal Grade 1 Grade 2 Tenderness/discomfort Normal Grade 1 Grade 2 Tenderness/discomfort Normal Grade 2 Erythema/redness	0 (0.0%) 1 (4.2%) 15 (62.5%) 8 (33.3%) 6 (25.0%) 16 (66.7%) 2 (8.3%) 2 (8.3%) 14 (58.3%) 8 (33.3%)
Local	Normal Grade 3 Any Normal Grade 1 Grade 2 Pain Normal Grade 1 Grade 2 Tenderness/discomfort Normal Grade 1 Grade 2 Tenderness/discomfort Normal Grade 2 Erythema/redness Normal	0 (0.0%) 1 (4.2%) 15 (62.5%) 8 (33.3%) 6 (25.0%) 16 (66.7%) 2 (8.3%) 2 (8.3%) 14 (58.3%) 8 (33.3%)
Local	Normal Grade 3 Any Normal Grade 1 Grade 2 Pain Normal Grade 1 Grade 2 Tenderness/discomfort Normal Grade 1 Grade 2 Erythema/redness Normal Grade 1 Grade 2	0 (0.0%) 1 (4.2%) 15 (62.5%) 8 (33.3%) 6 (25.0%) 16 (66.7%) 2 (8.3%) 2 (8.3%) 14 (58.3%) 8 (33.3%) 23 (95.8%) 1 (4.2%)
Local	Normal Grade 3 Any Normal Grade 1 Grade 2 Pain Normal Grade 1 Grade 2 Tenderness/discomfort Normal Grade 1 Grade 2 Erythema/redness Normal Grade 1	0 (0.0%) 1 (4.2%) 15 (62.5%) 8 (33.3%) 6 (25.0%) 16 (66.7%) 2 (8.3%) 2 (8.3%) 14 (58.3%) 8 (33.3%) 23 (95.8%) 1 (4.2%)

